10.2 Trial Assessments

Written informed consent must be obtained before any of the procedures listed below are performed. An explanation of the trial and discussion of the possible risks and discomforts will be given by the Investigator or appropriate designee. Only those patients who fulfill all eligibility criteria will be entered into the trial.

Ocular assessments performed at Month 12 and Month 18 (and at an EW visit, if performed) should be performed pre-injection (as applicable) on both eyes (OU). Ocular assessments at all other trial visits are performed only on the SE.

Screening and Day 1 (ISEE2008 Baseline) assessments were performed as part of enrollment into Study ISEE2008 (GATHER2), and therefore, are not repeated for this OLE trial. Refer to the ISEE2008 (GATHER2) protocol for Screening and Day 1 assessments and corresponding procedures (Section 10.2 and Section 7, respectively).

The following assessments, as outlined in the Study Assessments Chart (see [Section 3](#)), will be performed on the days specified below.

Note:

- **IVT injection is contraindicated in patients with active ocular or peri-ocular infections and in patients with active intraocular inflammation.**
- **Concomitant medications should be assessed at every trial visit.**
- **AEs and serious AEs (SAEs) should be assessed starting at Month 1 (first visit of this OLE trial) after the first dose of study drug until 30 days after the last dose of study drug or until the last follow up visit of the trial, whichever comes later.**

Month 1

- **Pre-Injection:**

- Informed consent (must be signed before any other assessments are performed at Month 1)
- Urine pregnancy test (if applicable)
- Immunogenicity and PK sampling
- Refraction
- BCVA (4 meters) using ETDRS chart (SE)
- LLVA
- Tonometry (SE)
- Full ophthalmologic examination (SE)
- Color fundus photography (SE)
- Fundus autofluorescence (SE)
- Optical coherence tomography (SE)
- Treatment with IVT avacincaptad pegol 2 mg

- **Post-injection:**

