4.5 Exploratory Endpoint(s) Analysis

The exploratory endpoints are ophthalmic findings. All the assessments will be mapped to a scheduled visit. The mapping rule is provided in Table 2 for BCVA, OE and IOP and Table 3 for LLVA.

Best Corrected Visual Acuity (BCVA)

The score and the change from baseline of BCVA (ETDRS letters) at each analysis visit will be summarized descriptively by cohort for the FAS.

Low Luminance Visual Acuity (LLVA)

The score and the change from baseline of LLVA (ETDRS letters) at each analysis visit will be summarized descriptively by cohort for the FAS.

Low Luminance Deficits (LLD)

The score and the change from baseline of LLD (ETDRS letters) at each analysis visit will be summarized descriptively by cohort for the FAS, where LLD is calculated by the difference of BCVA and LLVA at a same visit.

Intraocular Pressure (IOP)

Baseline IOP is the pre-injection IOP value before the first study drug administration in this study.

Pre-injection IOP is defined as the last IOP value before an injection on a visit with injection (whether ACP or other treatment) or the last IOP value on a visit without an injection.

Post-injection IOP is defined as the IOP value after one injection that is closest in time to the protocol-specified post-injection timepoint (but at least 30 minutes post-injection).

Pre-injection and post-injection IOPs at each analysis visit will be summarized descriptively by cohort for the SAF with in one table. The number and percentage of participants in categories of pre-injection IOP value (≤ 21 mmHg, 22-29 mmHg, 30-34 mmHg, ≥ 35 mmHg) will be summarized at each analysis visit for each cohort.

The change from baseline of pre-injection IOPs will be summarized at each analysis visit for each cohort.

Change of IOP at each analysis visit is the difference between the post-injection and pre-injection IOPs. Change of IOP at each analysis visit will also be summarized descriptively for each cohort. The number and percentage of participants in categories of change of IOP (≤ 0 mmHg, 1-5 mmHg, 6-10 mmHg, >10 mmHg) will be summarized at each analysis visit for each cohort.

The number and percentage of participants who experienced the following events will be summarized for each cohort. The events are:

- Either pre-injection or post-injection IOP ≥ 35 mmHg,
- Had a paracentesis and
- Received IOP-lowering medications.

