4.10 Additional Conventions

4.10.1 Analysis Windows

Study Day for analysis windows will be calculated as: Date of visit/assessment – first dose of study drug in this study + 1.

The assignment of analysis visit will be consistent across all by-visit analysis datasets, and will follow the respective step-by-step algorithm:

- All assessment visits will be windowed, per the below tables, regardless of SE/FE, scheduled/unscheduled status, injection date, or pre/post-injection status.
- Baseline derivations will follow the definitions as stated in Section 4.1.

An analysis flag will be created for each record by following rules.

- **General Rules for Analysis Flags**
 - Scheduled visits falling into their respective analysis window will be prioritized over unscheduled visits.
 - If multiple observations still exist, the observation closest to the scheduled day will be selected for the analysis visit.
 - If there are two observations that have the same distance from the scheduled day, the value that is after the scheduled day will be selected for the analysis visit.
 - If more than one observation (excluding OE/IOP observation) is made on the same day, an average value for continuous measurement, or the worst value for categorical measurement, will be used for the analysis visit.
 - Any additional rules will be prespecified and documented in the TLF specifications.
- **Additional Rules for OE/IOP Analysis Flags except those in the Analysis Visit Month 18**
 - The OE/IOP records on a visit falling into its respective analysis window and with at least one SE ACP pre-injection and one SE ACP post-injection records will be firstly selected.
 - If there are no OE/IOP records satisfying the first rule, the records on a visit (whether scheduled or unscheduled) and with at least one SE ACP pre-injection and on SE ACP post-injection records will be selected.
 - If there is no OE/IOP records satisfying the above two rules, the records will be selected from a visit day (whether scheduled or unscheduled) that contain at least one pre-injection or one post-injection record to separately summarize the pre-injection and post-injection IOPs.
 - The closest OE/IOP observation to the target time will be selected for analysis.
 - If both Tonopen and Goldmann measurement are recorded available at the same time per CRF, the Goldmann measurement will be prioritized.

Listings will include all scheduled, unscheduled, and early withdrawal data.

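### The IOP selection rules prefer injected visits, so a visit at which the dose was withheld can drop out of the by-visit pre-injection IOP summaries

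*SAP*

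**What the plan says.** SAP 4.10.1 first gives General Rules for picking one record per analysis window. Among them: "Scheduled visits falling into their respective analysis window will be prioritized over unscheduled visits"; after that, the observation closest to the scheduled day is taken. Whether an injection was given plays no part.

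A second set follows, headed "Additional Rules for OE/IOP Analysis Flags except those in the Analysis Visit Month 18". It has three ordered steps:

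1. Records on a visit in its own window "with at least one SE ACP pre-injection and one SE ACP post-injection records will be firstly selected".
2. "If there are no OE/IOP records satisfying the first rule, the records on a visit (whether scheduled or unscheduled") are taken, again provided that they include a study-eye ACP pre/post pair.
3. "If there is no OE/IOP records satisfying the above two rules, the records will be selected from a visit day" that has at least one pre-injection or one post-injection record.

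SAP 4.5 defines pre-injection IOP as the last value before an injection, "or the last IOP value on a visit without an injection". The planned by-visit outputs include "The number and percentage of participants in categories of pre-injection IOP value" (cut at 21, 29 and 34 mmHg), the level, the change from baseline, and a plot of that mean change.

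Protocol 10.2 states: "IVT injection is contraindicated in patients with active ocular or peri-ocular infections and in patients with active intraocular inflammation".

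**The concern.** Whether a visit contains an ACP pre/post pair can depend on the condition of the eye that day. A rule that ranks paired visits first therefore ties the choice of record to the state of the eye, and IOP is part of that state. Pairing is needed to compute the post-minus-pre change. It is not needed to report the pre-injection level, its categories or its change from baseline, because SAP 4.5 treats a reading from an uninjected visit as a full pre-injection value.

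At stake is whether the by-visit IOP tables describe all eyes attending in a window or, wherever a choice exists, eyes judged fit to inject. A pre-dose reading of 30-34 mmHg has few other places to be counted. The IOP events of special interest in SAP 4.6.2 are post-injection, and the event counts in SAP 4.5 start at 35 mmHg.

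**Working it through.** **Inputs.** Scheduled days and windows: SAP Table 2. Protocol visit window of ±7 days for Months 2-17: Protocol 10.2. Planned enrolment of about 280: SAP 4.9. I read rule 2 as applying within one analysis window, since SAP 4.10.1 assigns every record to a window before any flag is set.

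**1. Table 2 reproduced.** Scheduled day = round(30.4375 × (month − 1)). Month 9: 30.4375 × 8 = 243.5, rounded to 244. All of Months 2-18 match. Lower bound = round(30.4375 × (month − 1.5)), the midpoint of unrounded days. Month 9: 30.4375 × 7.5 = 228.3, so 228. Month 10: 30.4375 × 8.5 = 258.7, so 259, which makes the Month 9 upper bound 258. All 16 lower bounds for Months 3-18 match. Using rounded days instead moves Months 7, 9, 14 and 16 by one day, which does not affect the example below.

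**2. The rules applied to one case.** Month 9: dose withheld on Day 244 and given at an unscheduled visit on Day 251. Day 251 is the last day the protocol allows (244 + 7). IOP values of 34 and 18 mmHg are assumed.

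| Step | Day 244 (scheduled, no injection, IOP 34) | Day 251 (unscheduled, injected, IOP 18) |
|---|---|---|
| Rule 1 | no pair | not scheduled |
| Rule 2 | no pair | selected |
| Rule 3 | not reached | not reached |
| General Rules instead | selected | not selected |

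The current rules report 18 mmHg (category 21 or below). The General Rules would report 34 mmHg (category 30-34).

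**3. When a later dose displaces the withheld visit.** Upper bound minus scheduled day is 15 in Months 2, 4 and 11 and 14 in the other 13 windows. For a dose withheld exactly on the scheduled day:

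- given up to 14 days later: displaced in 16 of 16 windows;
- given 15 days later: 3 of 16;
- given 21 days later: 0 of 16.

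Letting the withheld visit fall on any day within ±7 gives 16 × 15 = 240 combinations:

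| Delay (days) | Displaced | Share |
|---|---|---|
| 7 | 240/240 | 100% |
| 10 | 195/240 | 81% |
| 14 | 131/240 | 55% |
| 21 | 19/240 | 8% |
| 23 or more | 0/240 | 0% |

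Every ±7-day protocol window lies wholly inside its own analysis window. A dose deferred within the protocol window therefore always displaces the withheld visit. A dose skipped to the next monthly visit falls in the next analysis window, and rule 3 keeps the withheld visit.

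**4. Which outputs use the flagged record.** Affected: by-visit pre-injection IOP level, categories, change from baseline and its plot, Months 2-17. Not affected: the examination shift table, which runs from Baseline to Month 18 (Month 18 is exempt and Baseline has its own definition); the listings, which hold all visits; and the AE and AESI tables. Unclear: the participant count of IOP of 35 mmHg or more, because SAP 4.5 does not say whether it uses all records or only flagged ones.

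**5. Scale only.** The documents give no deferral rate. Assume that 1 to 6 participants at one visit have the dose withheld with IOP of 30 mmHg or more, that no other eye is that high, and that all 280 attend. The true share is 1/280 = 0.36% to 6/280 = 2.14%. If all are injected later in the window, the table shows 0%; if half are, 0.18% to 1.07%. With the assumed 34 and 18 mmHg and all displaced, the mean falls by 16/280 = 0.06 to 6 × 16/280 = 0.34 mmHg.

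**The case against.** The strongest reply is that the documented reason for withholding and the affected table do not meet. The protocol names infection and intraocular inflammation as contraindications, not raised pressure. It gives no pre-injection IOP threshold for withholding ACP: the 30 mmHg limit in Protocol 7.2 governs leaving the clinic, and the 21 mmHg limit in Protocol 10.3 governs a following anti-VEGF injection. Appendix 17.2 allows pressure-lowering drops before the injection, so a high reading need not lead to deferral. This stands. Deferral for pressure is a matter of investigator judgement, and for deferrals on other grounds the direction of any effect on IOP is unknown.

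A reader might also infer that inflamed eyes vanish from the examination results. They do not: the only tabulated post-baseline examination summary is the exempt Month 18 shift, and inflammation is captured as an AESI. Nor are abnormal pressures lost from the record, since the listings keep every visit and nothing in SAP 4.5 confines the 35 mmHg participant count to flagged records.

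The pairing rule has a purpose as well. Pre- and post-injection values share one table with their difference, and one visit day keeps them coherent. That justifies pairing for the difference, but not for summaries of the pre-injection value alone. IOP is exploratory and no hypothesis is tested, which limits the weight of the point without removing it.

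**Conclusion.** The point holds for the by-visit pre-injection IOP displays at Months 2-17. When a withheld dose is given later in the same analysis window, the rules replace the scheduled reading with one from a day on which the eye was judged fit to inject, although the SAP's own definition accepts the earlier reading. Where the deferral was for raised pressure, the bias is toward lower pre-dose IOP.

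The size cannot be derived from the documents and is probably small; the figures in step 5 rest on assumed counts and pressures. The finding rests on reading rule 2 within the window and on doses being delayed rather than skipped. The documents do not support the stronger reading that the plan systematically hides high pressures or inflammation: no pressure-based withholding rule exists, a rate of deferral for any eye finding is not a rate of high IOP, and the AE, AESI and listing outputs are intact. It is a cheap improvement to an exploratory safety display.

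**What to change.** In SAP 4.10.1, require the study-eye ACP pre/post pair only for the post-minus-pre IOP change and its categories. For the pre-injection IOP level, categories, change from baseline and plot, select the visit by the General Rules whether or not ACP was given. In SAP 4.5, state that the participant-level count of IOP of 35 mmHg or more uses all records, not only flagged ones.

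The cost is SAP wording and a programming change before database lock; no new data are needed. In the few windows with a deferred dose, the pre-injection summary and the paired change will come from different days, so a footnote should say so. The General Rules retain the withheld visit when it is entered as the scheduled visit, so the programming specification should confirm how such visits are labelled.

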4.10.2 Imputation Rules for Incomplete Dates

Assumptions for missing or partially missing dates for important variables will be made to allow inclusion of appropriate data records in the analyses. In general, the assumptions about the missing or partially missing dates, when needed, are made conservatively to avoid overestimation of treatment effect and underestimation of adverse effects.

If a medication date or time is missing or partially missing, so it cannot be determined whether it was taken prior or concomitantly, it will be considered both as a prior and a concomitant medication.

If the partial AE onset date information does not indicate whether the AE started prior to treatment or after treatment, the AE will be classified as after the start of treatment.

In case of missing or partial start and stop dates for concomitant medications, the following rules will be used:

- If the start date is missing or partial:
 - If the month is missing, use January.
 - If the day is missing, use the first day of the month under consideration.
 - If the year is missing, use year of the informed consent date.
 - If the entire date is missing, use informed consent date.
- If the stop date is missing or partial:
 - If the month is missing, use December.
 - If the day is missing, use the last day of the month under consideration.
 - If the year or the entire date is missing, set the stop date to December 31st, 2099.
- If the imputed start date is after the stop date, then the imputed start date will be 1 day prior to the stop date.
- For AEs, a missing or incomplete onset date will be imputed according to the following conventions.
- If an onset date is missing, the imputed onset date will be the date of first dose of study drug.
- If only the year is known for the AE onset date, the imputed onset date will be the latest of the following non-missing dates:
 - Date of first dose of study drug, and
 - January 1 of the year of AE onset date.
- If only the month and year is known for the onset date, set the surrogate onset date to the first day of that month and then apply the following rules.
- If the month and year of the onset date is prior to the month and year of the first dose of study drug, then the surrogate onset date will be the imputed onset date.
- If the month and year of the onset date is on or after the month and year of the first dose of study drug, then the imputed onset date will be the latest of the following non-missing dates:

- Date of first dose of study drug, and
- Surrogate onset date.
- If the imputed onset date is after the adverse event end date, the imputed onset date will be the same as the adverse event end date.

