4.6.1 Adverse Events

All AEs will be coded in MedDRA. AE analysis will be based on the SAF.

A treatment-emergent adverse event (TEAE) is defined as an AE starting after the first administration of the study drug in this study until 30 days after the last administration of the study drug or until the last follow-up visit required by the protocol, whichever comes later.

An overview table to report the number and percentage of participants and number of events will include but not limited to the following:

- TEAEs,
- Drug related TEAEs,
- Serious TEAEs,
- Serious drug related TEAEs,
- TEAEs leading to withdrawal of study drug,
- Drug-related TEAEs leading to withdrawal of study drug,
- Severe TEAEs,
- TEAEs leading to death,
- Drug related TEAEs leading to death,
- Deaths.

An additional overview of TEAEs will be provided which displays the overall summary of TEAEs by three categories (SE, FE, and non-ocular).

The number and percentage of participants with TEAEs, as classified by SOC and PT will be summarized for each cohort. Summaries will be provided for the following:

- TEAEs,
- TEAEs with frequency of $\geq 5\%$ in any cohort,
- TEAEs with frequency of $\geq 2\%$ in any cohort,
- Non-serious TEAEs with frequency of $\geq 5\%$ in any cohort,
- Study drug related TEAEs,

- Injection procedure related TEAEs,
- Serious TEAEs,
- Serious study drug related TEAEs,
- Serious injection procedure related TEAEs,
- TEAEs leading to withdrawal of study drug,
- Study drug related TEAEs leading to withdrawal of study drug,
- Injection procedure related TEAEs leading to withdrawal of study drug,
- TEAEs leading to death,
- Study drug related TEAEs leading to death,
- Injection procedure related TEAEs leading to death.

Ocular TEAEs have been defined as TEAEs linked to the “Eye Disorders” SOC or the “Intraocular Pressure Increased” PT.

The number and percentage of participants with ocular TEAEs or non-ocular TEAEs, as classified by SOC and PT, will be summarized for each cohort. Summaries will be provided for those including but not limited to the following:

- Ocular TEAEs by SE and FE,
- Ocular TEAEs with frequency of $\geq 2\%$ in any cohort (by PT),
- Non-ocular TEAEs with frequency of $\geq 2\%$ in any cohort (by PT),
- Study drug related Ocular TEAEs (SE),
- Injection procedure related Ocular TEAEs (SE),
- TEAEs with high level term of cataract conditions by SE and FE,
- Serious ocular TEAEs (SE),
- Serious study drug related ocular TEAEs (SE),

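### SAP 4.10.2: the year-only AE onset rule has no branch for a year before first dose, so an event known to predate treatment is dated to first dose

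*SAP*

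**What the plan says.** Four provisions of SAP 4.10.2 bear on a partly dated AE.

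- **General principle.** The default to after the start of treatment carries a condition: "If the partial AE onset date information does not indicate whether the AE started prior to treatment or after treatment".
- **Year-only rule.** "If only the year is known for the AE onset date, the imputed onset date will be the latest of the following non-missing dates". The candidates are the date of first dose and "January 1 of the year of AE onset date". No case is separated out for an earlier year.
- **Month-and-year rule.** The surrogate date is the first of the month. One branch applies under this condition: "If the month and year of the onset date is prior to the month and year of the first dose of study drug". In that branch the surrogate is kept, so the onset stays before first dose. Otherwise the later of first dose and the surrogate date is used.
- **End-date cap.** An imputed onset that falls later than the end of the AE is moved back to that end date.

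For a wholly absent date: "If an onset date is missing, the imputed onset date will be the date of first dose of study drug".

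In SAP 4.6.1, "A treatment-emergent adverse event (TEAE) is defined as an AE starting after the first administration of the study drug in this study". SAP 4.3 names AEs as the primary endpoint and refers to Section 4.6 for the analysis.

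**The concern.** An onset year before the first-dose year settles the order of events: the AE began before treatment. The condition in the general principle is therefore not met, and the event should stay pre-treatment. The year-only rule nevertheless moves it to the first-dose date, the same date that a wholly unknown onset receives. Had the site also recorded a month, the month-and-year rule would have kept the event before first dose. The classification thus turns on whether the month is missing and not on any doubt about the order.

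At stake is whether such an event counts in the TEAE tables. These carry the primary endpoint, and they include the tables limited to terms reaching 2% or 5% in any cohort.

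**Working it through.** **Inputs.** All rules come from SAP 4.10.2. First-dose dates of 10 January 2023 and 15 June 2023 and an onset year of 2022 are assumed for illustration; only the order of the dates matters.

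**Rules as formulas**, with F the first-dose date, Y the onset year, M the onset month and E the AE end date:

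- Year only: onset = max(F, 1 Jan Y).
- Month and year: onset = first of M/Y if M/Y precedes the month of F; otherwise max(F, first of M/Y).
- No date: onset = F.
- Cap, applied last: if onset > E, onset = E.

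If Y is before the year of F, then 1 Jan Y < F, so max(F, 1 Jan Y) = F whatever Y is.

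**Results**

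| Onset recorded | End date | F = 10 Jan 2023 | F = 15 Jun 2023 |
|---|---|---|---|
| 2022 | none, or 1 Sep 2023 | 10 Jan 2023 | 15 Jun 2023 |
| Nov 2022 | none, or 1 Sep 2023 | 1 Nov 2022 | 1 Nov 2022 |
| 2022 | 20 Dec 2022 | 20 Dec 2022 | 20 Dec 2022 |
| no date | none | 10 Jan 2023 | 15 Jun 2023 |

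Every onset year tried from 2015 to 2022 gives F under the year-only rule when there is no end date. With the month known, 0 of the 12 months of 2022 give an onset on or after F. The cap restores the right order only when the event ended before first dose. Events that are ongoing, that end on or after first dose, or that have no end date stay at F.

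**Size per record.** One participant wrongly counted under a term adds 1/280 = 0.36 percentage points in the total, using the planned enrolment. The documents give no cohort sizes. If a cohort held 60 to 80 participants (an assumption), one extra participant would add 1/80 = 1.25 to 1/60 = 1.67 points. Going from one participant to two would take a term from 1.7% to 3.3% at 60, or from 1.25% to 2.5% at 80, across the 2% line in both cases. The number of affected records cannot be derived from the documents.

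**With an earlier-year branch** (1 Jan Y when Y precedes the year of F), onset year 2022 gives 1 Jan 2022, which is pre-treatment in every scenario. Onset year 2023 still gives F, and onset year 2024 still gives 1 Jan 2024.

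**The case against.** **The rule is deliberately conservative.** The section does aim to avoid understating adverse effects, and the gap can only over-count TEAEs. But the same aim governs the month-and-year rule, which leaves earlier-month events pre-treatment, and the general principle keeps its default for dates that settle nothing. An earlier year settles the matter, so this defence does not stand.

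**The case should hardly arise.** This stands. Protocol Section 3 (footnote j) and Section 12.2 start AE recording after the first dose. SAP 4.2.3 places events before first dose, including the history recorded in ISEE2008, in ocular or medical history. A reader might infer that long-standing conditions carried over from ISEE2008 will swell the primary tables. The documents do not support that: nothing says that such conditions enter the AE dataset. A reader might also take the planned listing of non-TEAEs in SAP 4.6.1 as proof that AEs with onset before first dose are expected. It is not, because the TEAE window also has an upper end, and Protocol 12.5 provides for reporting some SAEs after the trial. The earlier-month branch of SAP 4.10.2 is the better evidence that the SAP allows for such onsets.

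**Treatment-emergent status is not certain.** This stands in part. The TEAE definition says after the first administration, and the imputed date equals the first-dose date. The SAP does not state how a same-day imputed onset is classified, nor whether the imputed date overrides the general principle applied to the raw partial date. The status is inferred: a wholly missing onset gets the same date, and the default for uninformative dates works only if that date counts as after the start of treatment.

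**Some of these records may be genuine.** Protocol 12.1 counts the worsening of a pre-existing illness as an AE. An old year on a record entered after dosing may be the year of the underlying illness. This is a fair point and bears on the cost of the fix.

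**Conclusion.** The rule is inconsistent as written. For an onset year before the first-dose year it gives the first-dose date, against the general principle and the month-and-year rule of the same section, unless the AE ended before first dose. That such events would then be tabulated as TEAEs rests on the inference that an imputed first-dose date counts as treatment-emergent.

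The practical effect should be small. The collection rules leave few such records, the error runs only towards over-counting, and SAP Section 2 rules out hypothesis tests, so no inference changes. The documents do not support a claim of material distortion of the primary endpoint. The crossing of the 2% line depends on assumed cohort sizes. This is a minor consistency correction, worth making because the rule feeds the classification behind the primary endpoint.

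**What to change.** Replace the year-only rule in SAP 4.10.2 with:

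*If only the year is known and it is before the year of first dose, the imputed onset date is 1 January of that year; otherwise use the later of the first-dose date and 1 January of that year.*

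Keep the existing end-date cap. The choice of 1 January follows the month-and-year rule, which uses the first day of the known period.

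The cost is one sentence and one line of derivation code. The downside is that a true post-dose worsening entered with the year of the underlying illness would become a non-TEAE, as already happens under the month-and-year rule when an earlier month is entered. To limit this, query AE records whose onset year precedes first dose before database lock, so that the site confirms or corrects the date. If the SAP is already final, document the change in the Clinical Study Report, as SAP Section 1 provides.
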